7.1 Data entry

Information extracted from the subject's medical records includes date of service, subject name, date of birth, medical record number, age, gender, height, weight, data pertaining to the subject's pain, opioid consumption and ASA classification.

All study data will be collected by a study team member on a standardized case report form (CRF) and transferred to an electronic Microsoft Excel spreadsheet suitable for export in coded format to a statistical analysis program. Data entry into electronic format will take place on a private computer away from potential viewing by non-study personnel. The paper and electronic data will be kept in the primary investigator's locked office in the Department of Anesthesiology. The computer will be pass-coded and linked to a secure Anesthesia Department server to allow access only to approved study personnel. All identifiable data will be destroyed as soon as it is no longer required after study publication and/or study conclusion, and de-identified data will be retained for 7 years per UW-Madison best practices.

7.2 Subject withdrawals

At any point prior to or during the intervention period, the subject's clinical care team or a study physician may decide the subject should be withdrawn from the study. Additionally, a subject may at any point elect to withdraw themselves from the study. If a subject is withdrawn from the study for any reason the subject will then be followed according to standard of care follow-up.

Study intervention will immediately stop and subject's clinical care team and a study physician will be immediately notified if the subject suffers a severe adverse perioperative outcome.

In the event the study method is terminated, the reason for termination will be documented on a case report form.

8. Data analysis and statistical considerations

All data will be summarized using standard descriptive statistics, including mean, standard deviation, minimum, maximum, median, inter-quartile range, and confidence intervals, as appropriate. The data will be presented graphically (where possible) using scatter plots, profile plots, or histograms. Data analyses will be performed on an intent-to-treat basis based upon assignment to a treatment arm using SAS (SAS Institute Inc., Cary, NC; version 8.2 or greater) or other statistical software. The primary analysis will consist of comparing the two groups for superiority. For all tests, statistical significance will be defined as a p-value less than 0.05. Repeated measures ANOVA will be used to analyze comparisons made across multiple time points. Patients with missing longitudinal data will be handled by either using data imputation methods to replace the missing data or via alternative analyses tolerant of missing data values. Holm-Bonferroni correction will be used to control familywise error rates for comparisons across multiple time points.

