After completion of pre-operative check in and consent is obtained by the staff anesthesiologist, the subject will be randomized to receive or not receive QLB. Randomization will be determined by opening a sequential, pre-sealed envelope with the group assignment designated within. If assigned to the intervention arm, they will then be prepped for QLB.

Quadratus Lumborum Block Procedure:

The block will be performed in the preoperative holding room as is standard practice at UW Health at the American Center. An intravenous catheter will be placed, and the subject will be pre-medicated with midazolam and/or fentanyl as needed at the discretion of the staff anesthesiologist.

Quadratus lumborum blockade will be performed after positioning the patient in the lateral decubitus position with the assistance of ultrasound guidance in the mid-abdomen posterior to the mid-axillary line. A Stimuplex needle (B. Braun Medical Inc., Melsungen, Germany) will be inserted in-plane to the ultrasound probe until the tip of the needle is appropriately positioned. Thirty milliliters of 0.25% bupivacaine will be injected under ultrasound guidance after negative aspiration. The procedure will then be repeated on the opposite side, maintaining sterility and, again, injecting 30 mL of 0.25% bupivacaine. The Bupivacaine mixture will be mixed with 2.5mcg epinephrine/ml of solution as an intravascular marker which is standard in most peripheral nerve blocks. In a situation where a patient is less than 60kg, a weight-based adjustment will be made to adjust dosing to the clinically accepted standard of 0.25mg/kg of bupivacaine. In the rare event that sonographic views are unobtainable, the patient will be excluded from the study. This outcome is unlikely to be clinically significant as qualification for laparoscopic ventral hernia repair has its own cutoff for body mass index and blocks are very rarely abandoned. However, for patient safety, we reserve the right to abandon a block.

During the Surgical Procedure:

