The patient will be contacted via phone at 24 hours, 48 hours, and 7 days to assess satisfaction with regional anesthesia, pain at rest, pain with activity, opioid consumption, nausea, pain disturbing sleep, and location of most severe pain. Duration of hospitalization will be obtained from review of medical record. Subjects with new or persistent complaints at 7 days post-surgery that could be related to the study procedures will be offered continued follow-up by telephone. Follow-up procedures would depend greatly on the clinical presentation but could include imaging, specialist consultation or surgical intervention. Subjects without complaints will be given appropriate information for contacting the research team if such complaints arise.

Concomitant Medications:

Analgesic and anti-emetic requirements for block placement, intraoperatively, and in PACU will be extracted from the patient's electronic medical record.

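### Section 7.2 sends every withdrawn subject to standard-of-care follow-up and does not provide for further study assessments, so the POD1 pain score would probably be missing for anyone withdrawn before the 24-hour call

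*Combined protocol and SAP*

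**What the plan says.** Section 7.2 gives a discretionary power: "the subject's clinical care team or a study physician may decide the subject should be withdrawn from the study". No criteria are given. The time limit on this power is worded as "At any point prior to or during the intervention period", and that period is not defined. Subjects may withdraw themselves at any time. For both routes the consequence is the same: "If a subject is withdrawn from the study for any reason the subject will then be followed according to standard of care follow-up".

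A separate paragraph of 7.2 deals with severe events. The study intervention stops, and "a study physician will be immediately notified if the subject suffers a severe adverse perioperative outcome". That paragraph does not say whether the subject remains in the study.

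The primary endpoint is resting NRS on POD1 (Sections 1.2 and 8.1). Under the follow-up heading of Section 7, "The patient will be contacted via phone at 24 hours, 48 hours, and 7 days", and pain at rest is one of the items asked. The Schedule of Activities marks the 24-hour pain questionnaire as a study item (X), not as SOC.

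Section 7 places randomisation before preparation for the block. Its block-procedure text then excludes a patient whose ultrasound views cannot be obtained, and adds that "for patient safety, we reserve the right to abandon a block".

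Section 8 states: "Data analyses will be performed on an intent-to-treat basis based upon assignment to a treatment arm". On missing values it says: "Patients with missing longitudinal data will be handled by either using data imputation methods to replace the missing data", or alternatively an analysis that tolerates missing values. The last bullet of Section 11.1 leaves the data of a subject who withdraws early out of the final study.

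**The concern.** The block is a single preoperative procedure. Once it has been given, or for any control subject, no study intervention remains to be stopped, and the main practical effect of withdrawal is that study measurement ends. If that happens before the 24-hour call, the plan has no stated way of obtaining the primary outcome.

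The loss need not be balanced. Only a subject assigned to QLB can have a block abandoned or ultrasound views that cannot be obtained. If those subjects would have reported more pain on POD1 than the other QLB subjects, a comparison of completers makes the block look better than a comparison of everyone randomised. The intent-to-treat estimate would then depend on imputing scores that an already planned call could have supplied.

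**Working it through.** **Inputs.** From Section 8.1: difference 2 NRS, SD 2.2, type 1 error 0.05, power 80%, 21 per arm needed, 24 per arm enrolled. From Section 5: 1:1 allocation. Sidedness is not stated; the two-sided calculation reproduces the plan's figure.

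**The plan's own figure.** The normal approximation gives 2 × (1.960 + 0.842)² × (2.2/2)² = 2 × 7.85 × 1.21 = 19.0, or 19 per arm. The noncentral t calculation gives 20.002, rounded up to 21, which matches the plan. The implied loss allowance is 1 − 21/24 = 12.5%, or 3 per arm.

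**Power.** By the two-sample t-test, power is 86.9% with 24 per arm, 84.5% with 21 against 24, and 82.0% with 21 per arm. Losing the 3 per arm allowed for does not take power below 80%.

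**Would the POD1 score be lost?**
- Section 7 calls pain a standard-of-care assessment only in the PACU. The 24-hour score comes from a study contact.
- Section 7.1 also takes pain data from the medical record. Section 1.1 says laparoscopic repairs are typically outpatient, so a resting score at 24 hours would often not be there.
- A subject withdrawn in the holding area has only the preoperative resting score, which gives imputation or a repeated-measures model very little to work from. Section 8 chooses no method, and its wording covers longitudinal data, which may not extend to a single POD1 comparison.

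**Possible bias.** Assumptions, none of them in the documents: *w* = 1 to 3 subjects are lost from the QLB arm only, and their POD1 NRS would average *d* = 2 to 4 points above the QLB completers. If the completer mean is *m*, the mean of all 24 is *m* + *w* × *d*/24, so the completer mean is too low by *w* × *d*/24.

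| Lost (*w*) | *d* = 2 | *d* = 3 | *d* = 4 |
|---|---|---|---|
| 1 | 0.08 | 0.13 | 0.17 |
| 2 | 0.17 | 0.25 | 0.33 |
| 3 | 0.25 | 0.38 | 0.50 |

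Against the 2-point target the range is 0.083/2 = 4% to 0.50/2 = 25%.

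**False-positive rate.** With the same losses, no true effect, SD 2.2 and a complete control arm of 24, simulation (40,000 runs, two-sided t-test at 0.05) gives rejection rates from 5.1% (*w* = 1, *d* = 2) to 11.3% (*w* = 3, *d* = 4).

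**The case against.** Several stronger readings are tempting, and the documents do not support them.

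- **A severe perioperative outcome removes the subject from the study.** A reader might infer this because the paragraph sits under withdrawals. The text only stops the intervention and requires notification. The subject's study status is left unclear, which is a reason to clarify it.
- **The POD1 score is never collected after withdrawal.** A subject who leaves after the 24-hour call already has one, and the medical record may hold one for others.
- **Intent-to-treat cannot be carried out.** Section 8 allows imputation or a missing-tolerant analysis, and Section 8.1 adds 3 subjects per arm for dropout. Incomplete follow-up weakens intent-to-treat without preventing it. The 3 extra subjects protect power but do nothing about bias.
- **An unblinded team can remove subjects who are doing badly.** Knowledge of the arm is a reasonable inference: the envelope is opened before surgery, the block is given in the holding room and no sham is described. The documents do not state the care team's blinding status. Team withdrawal is also limited to before or during the intervention period. If that period is only the block, the power lapses before any postoperative pain is seen.
- **Every abandoned block leads to withdrawal.** For unobtainable views, Section 7 prescribes exclusion. For other abandoned blocks nothing requires withdrawal, but no other course is stated either.

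The size of the effect can also fairly be challenged. Section 7 describes abandoned blocks as very rare, and the allowance of 3 per arm covers dropout of every kind in both arms. An excess of 2 points is what a subject without a working block would show if the target effect were true. The 4-point figure has no source in the documents. One loss at 2 points is 0.08 NRS, and the rejection rate stays near nominal.

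What stands is that no sentence in the protocol provides for study assessments after withdrawal, and Section 11.1 goes further by discarding what was collected.

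**Conclusion.** The concern holds as a gap in the plan. Withdrawal for any reason leads to standard-of-care follow-up, continued outcome collection is not provided for, and the primary endpoint would probably be missing for subjects withdrawn before the 24-hour call. With the Section 11.1 exclusion and the exclusion for unobtainable views after randomisation, this undermines the intent-to-treat analysis in Section 8. Because block-related losses can occur only in the QLB arm, the missingness can differ by arm.

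The illustrated bias of 0.08 to 0.50 NRS rests wholly on the assumed number of one-arm losses and their assumed excess pain. The upper end is a worst case, and the documents do not show that losses on that scale will occur. The case for change rests on the possibility of bias together with a very low cost of avoiding it.

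**What to change.** Rewrite Section 7.2 to separate two events:

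- **(a) The block is stopped, abandoned or not completed.** The subject stays in the study in the assigned arm and still receives the PACU, 24-hour, 48-hour and 7-day assessments.
- **(b) The subject withdraws consent to further contact.** Only this ends the calls. Data already collected and medical-record data are used as far as consent allows.

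State that the severe-outcome paragraph does not by itself end study follow-up, and record on the CRF which event applied. Section 7.2 already asks for a reason when the study method is terminated, so this extends an existing record.

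Two other places must change with it. Delete the Section 11.1 sentence that leaves out withdrawn subjects' data, since it would otherwise contradict (b). Reconcile the Section 7 exclusion for unobtainable ultrasound views, which operates after randomisation, with analysis by assigned arm.

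Clinical care is unchanged. The cost is a wording amendment, one CRF item and at most three already planned calls for each affected subject.

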2.2 Secondary outcomes and endpoints

The secondary outcomes of this study are to compare the following perioperative variables:

Preoperative Variables:

- Baseline pain

Intraoperative Variables:

- Opioid consumption
- Additional analgesics
- Anti-emetic administration

PACU Variables:

- Pain at rest
- Pain with activity
- Nausea
- Numbness distribution
- Opioid consumption
- Time in PACU (duration)
- Time to discharge home (duration)
- Location of most severe pain

POD 1, 2, and 7 Variables:

- Pain at rest

- Pain with activity
- Opioid consumption in morphine equivalents
- Nausea necessitating treatment
- Location of most severe pain
- Satisfaction with perioperative care

3. Study design

This study is a prospective, single-center, randomized trial in which 48 subjects will be enrolled at the University of Wisconsin Hospitals and Clinics (UWHC). The details of the power analysis can be found below. These subjects must meet study eligibility criteria and be scheduled to undergo an elective laparoscopic ventral hernia repair. These subjects must also agree to undergo quadratus lumborum block for postoperative analgesia. Patients will be randomized to receive QLB in addition to medical management or medical management alone. Recovery characteristics, including pain scores, nausea, opioid consumption, duration of time in PACU and to discharge, will be evaluated.

4. Study population

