6.2 Recruitment and consent

For those patients meeting criteria, they will be approached by the anesthesiologist designated to care for them on the day of surgery. That anesthesiologist will then recruit the patient for the study in the pre-operative holding area. In order to ensure the candidate's privacy and confidentiality, the discussion will take place in pre-operative holding area with the cubicle's curtain and room door closed. In a tone of voice insufficient for others to overhear the conversation and in the presence of only those immediately accompanying the patient and those who are directly involved with the patient's care, the

candidate's eligibility will again be verified against the study enrollment criteria. For candidates with confirmed study enrollment eligibility, the study purpose, procedures, risks, benefits, and alternatives will then be discussed by a study staff member. The written information about the study provided to the candidate at the time of their check-in will be reviewed and they will be instructed to take up to 90 minutes to consider participation. A study member will conduct the informed consent discussion and obtain informed consent and a study physician will be available at all times for any consent-related questions. Any questions that the candidate may have will be answered. Undue coercion will be prevented by stressing that the potential subject does not have to agree to participation and that the future care of the potential subject will not change regardless of the decision about participation. If the candidate has no further questions and would like to participate, they will be asked to sign the written informed consent document.

7. Activities and measurements

Prior to the procedure:

The subject will be met in the preoperative area by a staff anesthesiologist, who interviews and examines the subject. A full explanation of general anesthesia and quadratus lumborum block, including risks, benefits, and alternatives, will be given and informed consent for anesthetic services obtained.

Subjects will be asked to rate their pain at rest using a Numerical Rating Scale (NRS) (0-10) where 0 represents no pain and 10 represents the worst pain imaginable.

Study Randomization:

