8.1 Sample size determination

The primary outcome for this study will compare resting NRS pain scores on POD1 between the QLB and medical management groups. A previous study of laparoscopic ventral hernia surgery reported an average POD1 pain score of 4.5 +/- 2.2 NRS (Fields et al, 2015). This average pain score is in keeping with our experience with patients after having laparoscopic ventral hernia surgery at UW-Madison. We feel that a reduction in pain of 2 NRS on POD1 would be meaningful for patients and their physician teams. Therefore, we will power this study to an effect size of 2 NRS. We will accept a type 1 error rate of 0.05 and 80% power. Using these metrics, the study will require a sample size of 21 patients in each group to

detect a statistical difference. To account for patients dropping out or not completing the study, we will enroll 24 patients in each group for a total of 48 patients.

9. Risks and benefits of trial participation

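### Preoperative resting NRS is collected but no test or covariate is named for the POD1 comparison; a prespecified baseline-adjusted ANCOVA costs at most about 1 point of power and gains if the correlation exceeds about 0.17

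*Combined protocol and SAP*

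**What the plan says.** Section 8.1 defines the primary comparison: "The primary outcome for this study will compare resting NRS pain scores on POD1 between the QLB and medical management groups". Section 8 says of its analysis only this: "The primary analysis will consist of comparing the two groups for superiority". It adds an intention-to-treat basis and a 0.05 significance threshold, but no test, model or covariate. The one model that section 8 names is reserved for something else: "Repeated measures ANOVA will be used to analyze comparisons made across multiple time points". A Holm-Bonferroni correction is attached to those multi-time-point comparisons.

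A baseline measurement exists. Section 7, under the activities before the procedure, states: "Subjects will be asked to rate their pain at rest using a Numerical Rating Scale (NRS) (0-10"). The next step in that section is randomisation, where "the subject will be randomized to receive or not receive QLB". The rating is therefore described as preceding allocation.

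Section 2.2 opens with "The secondary outcomes of this study are to compare the following perioperative variables", and the first item, under the preoperative variables, is "Baseline pain". No other use of the score is described.

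On size, section 8.1 requires 21 evaluable patients per group and then says "we will enroll 24 patients in each group for a total of 48 patients".

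**The concern.** The preoperative score measures the same quantity, on the same scale and under the same condition (rest), as the primary endpoint. It is fixed before allocation, so treatment cannot affect it. Such a score cannot be an outcome of the block. Its uses are to describe the arms at baseline and to explain part of the POD1 variance.

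Two things are at stake. The first is precision: ANCOVA removes the share of POD1 variance that preoperative pain explains, so the confidence interval narrows if the correlation is not small. The second is prespecification. As written, a t test, an ANCOVA, or a POD1 contrast taken from the repeated measures model could each be presented as the primary result. Naming one closes that choice.

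Validity is not at stake. The type I error of an unadjusted test already allows for chance differences at baseline.

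**Working it through.** **Inputs.** From section 8.1: difference δ = 2 NRS, SD σ = 2.2, α = 0.05, target power 80%, n = 21 evaluable and 24 enrolled per arm. Section 5 gives 1:1 allocation. Sidedness is not stated; two-sided is assumed. The correlation r between preoperative and POD1 resting NRS is not in the documents and is assumed at 0, 0.2, 0.3 and 0.5.

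**Step 1: reproduce the plan's figure.** For a two-sided two-sample t test, power comes from the noncentral t with 2n − 2 degrees of freedom and noncentrality δ / (σ√(2/n)).

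- n = 20: 79.997%, just short of 80%.
- n = 21: noncentrality 2 / (2.2 × √(2/21)) = 2 / 0.679 = 2.95 on 40 df; power 81.98%.
- n = 24: power 86.92%.

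The smallest n reaching 80% is 21, exactly the plan's number. The normal approximation gives 19 two-sided and 15 one-sided, so the plan's figure corresponds to an unadjusted two-sided t test. The allowance from 21 to 24 implies 1 − 21/24 = 12.5% dropout.

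**Step 2: ANCOVA with one baseline covariate.** The residual SD is σ√(1 − r²), on 2n − 3 df. Given the observed baseline imbalance, expressed as a t statistic t_x, the squared standard error is

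σ²(1 − r²) × (2/n) × (1 + t_x²/(2n − 2)).

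Power is averaged over t_x following a t distribution with 2n − 2 df. The mean of the last factor is 1 + 1/(2n − 4), which is 1 + 1/38 at n = 21. This charges the method for chance imbalance as well as for the lost degree of freedom.

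| Analysis | Power, n = 21 | 95% CI half-width | Power, n = 24 | 95% CI half-width |
|---|---|---|---|---|
| Unadjusted t test | 81.98% | 1.37 | 86.92% | 1.28 |
| ANCOVA, r = 0 | 80.95% | 1.39 | 86.15% | 1.29 |
| ANCOVA, r = 0.2 | 82.49% | 1.36 | 87.48% | 1.27 |
| ANCOVA, r = 0.3 | 84.43% | 1.33 | 89.13% | 1.23 |
| ANCOVA, r = 0.5 | 90.55% | 1.20 | 94.03% | 1.12 |

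**Step 3: cost, gain and break-even.**

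- Worst case (r = 0): 81.98 − 80.95 = 1.03 points at 21 per arm; 86.92 − 86.15 = 0.77, about 0.8 point, at 24.
- r = 0.3: gain of 84.43 − 81.98 = 2.45 points at 21; 89.13 − 86.92 = 2.21 at 24.
- r = 0.5: gain of 90.55 − 81.98 = 8.57 points at 21; 94.03 − 86.92 = 7.11 at 24.
- Break-even: r = 0.163 at 21 per arm and 0.152 at 24.

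Counting only the lost degree of freedom, the cost at 21 per arm would be about 0.05 point and the break-even about 0.04, so the figures above are the conservative ones.

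**Step 4: effective sample size at 21 per arm.** 21 / [(1 − r²)(1 + 1/38)] gives 20.5 at r = 0, 22.5 at r = 0.3 and 27.3 at r = 0.5.

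**Step 5: check on distribution.** Simulation with a normal baseline (200,000 trials per setting) gave 80.7, 82.5, 84.4 and 90.5% at 21 per arm for the four values of r. With a baseline assumed to be 60% zeros and otherwise 1 to 5 (100,000 trials), it gave 81.0, 82.4, 84.4 and 90.6%. A baseline score heavy in zeros does not change the picture at a given r.

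**The case against.** The plan is adequate without this change. Its sample size reproduces, and the unadjusted test meets the 80% target. A prespecified t test would settle equally well which result is primary. That stands, and it is why the point is an improvement and not a fault.

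The gain depends on a correlation that the documents do not supply, and there is reason to expect a modest one. Patients are elective, chronic opioid users and recurrent or multiple hernias are excluded (section 4.2), and POD1 pain follows new surgery with discretionary analgesia. This also stands. The r = 0.5 row should not be read as a forecast.

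The repeated measures ANOVA could be read as supplying the POD1 contrast, inside the Holm family. Section 8 confines that model to comparisons across several time points, while the primary comparison is at one. The possible reading is a further reason to name the primary test explicitly.

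The Schedule of Activities marks no pain questionnaire at Visit 1, so collection of the baseline rating is less secure than section 7 suggests. A line in the schedule answers this. How missing POD1 scores and withdrawn subjects are handled is a separate matter that this change does not settle.

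**Conclusion.** The point holds as a free improvement. A same-scale pre-randomisation score is already planned, and section 8 names neither a test nor a covariate for the POD1 comparison. Adjusting for the score costs at most about 1 point of power at 21 per arm (0.8 at 24), and even then power stays above 80%. It gains once the correlation exceeds about 0.17: roughly 2 points at r = 0.3, and 7 to 9 points if r were as high as 0.5. The figures rest on the plan's δ and SD, a two-sided test and an assumed range for r. If preoperative resting pain is low in most patients, r may be small and the gain nil.

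**What to change.** In section 8, replace the general statement of the primary analysis with wording such as:

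> The primary analysis is an ANCOVA of POD1 resting NRS on randomised arm and preoperative resting NRS, by intention to treat, reporting the QLB-minus-control difference with its 95% CI. A missing preoperative score is replaced by the mean of all observed preoperative scores, both arms pooled. The unadjusted difference is a sensitivity analysis.

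Add that this single test is separate from the repeated measures comparisons and their Holm-Bonferroni correction.

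In section 2.2, move baseline pain out of the secondary outcomes and into the baseline table, with no between-arm test.

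In section 7 and at Visit 1 of the Schedule of Activities, state that the preoperative rating is recorded before the envelope is opened. Section 7 already implies this order, so this is a clarification.

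The cost is a few lines of wording, one degree of freedom, and at most about 1 point of power if preoperative pain does not predict POD1 pain. Sample size is unchanged, and the score is one that section 7 already calls for.

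### Section 8 names repeated measures ANOVA and leaves the missing-score method open; some analyses this wording permits do not hold 5%, and one pre-specified mixed model would settle it

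*Combined protocol and SAP*

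**What the plan says.** The Schedule of Activities has pain assessed in PACU and at 24 hours, 48 hours and 7 days. For such series Section 8 states: "Repeated measures ANOVA will be used to analyze comparisons made across multiple time points". On gaps it states: "Patients with missing longitudinal data will be handled by either using data imputation methods to replace the missing data or via alternative analyses tolerant" (that is, of gaps).

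Section 8 names no imputation method, alternative model, covariance structure, sphericity correction, missingness assumption or sensitivity analysis, and no rule for choosing between the two routes. It applies Holm-Bonferroni across time points, sets the level ("For all tests, statistical significance will be defined as a p-value less than 0.05") and declares an intent-to-treat analysis. The primary comparison is described only as a superiority comparison of the two groups.

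Section 8.1 sizes the trial on resting NRS on POD1 alone and adds an allowance for loss: "To account for patients dropping out or not completing the study, we will enroll 24 patients in each group". Section 11.1 says that data from subjects who withdraw early will be left out.

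**The concern.** Classical repeated measures ANOVA assumes a restricted covariance across visits (sphericity), and a per-visit contrast that borrows its pooled error also assumes equal variances. Pain scores from PACU to day 7 may satisfy neither. Where variance falls over time, pooling makes the standard error too small early, when a block is most likely to look useful, and too large late.

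The classical analysis also needs a complete set of scores per patient, so the missing-data sentence decides what is actually run. It covers methods that keep the nominal level and methods that do not. The protocol describes no blinding, and Section 11.2 has the principal investigator look at study data every 3 months. A method chosen later could therefore be chosen with results in view. Section 8 gives POD1 no test of its own, so the longitudinal analysis could end up supplying the primary p-value.

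**Working it through.** **Inputs from the documents.** Effect: "we will power this study to an effect size of 2 NRS". The cited study "reported an average POD1 pain score of 4.5 +/- 2.2 NRS". Error rates: "We will accept a type 1 error rate of 0.05 and 80% power" (two-sided assumed). Result: "the study will require a sample size of 21 patients in each group", with 24 per group enrolled.

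**Inputs assumed.** SDs at visits other than POD1, within-patient correlations and the dropout pattern; the documents give none of these.

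**1. The plan's own figure.** A two-sample t-test with difference 2 and SD 2.2 has power 0.79997 at 20 per group and 0.820 at 21, so 21 reproduces. The implied loss is 1 - 21/24 = 12.5%, or 3 per arm. The plan states no rate.

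**2. Per-visit contrasts with pooled ANOVA error.** The pooled variance is the mean of the four visit variances, s². The size at visit j is about 2Φ(-1.96 × s/SD_j). For SDs 2.5/2.2/2.0/1.2, s² = (6.25 + 4.84 + 4.00 + 1.44)/4 = 4.1325 and s = 2.033. In PACU, 1.96 × 2.033/2.5 = 1.594, which gives 11.1%.

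| Assumed SDs (PACU/POD1/POD2/POD7) | s | PACU | POD1 | POD2 | POD7 |
|---|---|---|---|---|---|
| 2.5/2.2/2.0/1.2 | 2.033 | 11.1% | 7.0% | 4.6% | 0.1% |
| 2.2/2.2/2.0/1.5 | 1.996 | 7.5% | 7.5% | 5.1% | 0.9% |
| 2.8/2.2/1.8/1.0 | 2.057 | 15.0% | 6.7% | 2.5% | 0.0% |
| 2.2/2.2/2.2/2.0 | 2.152 | 5.5% | 5.5% | 5.5% | 3.5% |
| 2.2 at every visit | 2.200 | 5.0% | 5.0% | 5.0% | 5.0% |

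Simulated null trials (24 per arm; correlation 0.3 and 0.5 for the first three rows) agree: for the first row 11.2%, 7.0-7.3%, 4.8-5.1% and 0.1%; for equal SDs 4.7-5.2% at every visit. Estimating the variance separately at each visit held about 5% in the first three settings. Unequal variance is therefore the whole cause here.

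**3. Group-by-time test, no missing data** (4,000 null trials per setting, SD 2.2 unless stated):
- Uncorrected, compound symmetry: 5.0%.
- Uncorrected, AR(1) by visit at 0.6: 5.7%.
- Uncorrected, correlation decaying at 0.7 to 0.9 per day: 7.0-7.5%, and up to 8.0% with unequal SDs.
- Greenhouse-Geisser correction: 4.6-5.2%.
- Between-group main effect, which does not depend on sphericity: 4.5-5.3%.

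**4. Arm-mean replacement of 3 of 24 scores per arm at one visit.** Replaced scores add nothing to the sum of squares but raise n from 21 to 24 and the divisor from 20 to 23. The standard error shrinks by √[(20 × 21)/(23 × 24)] = √(420/552) = 0.872. The critical value 2.013 (46 df) then acts as 2.013 × 0.872 = 1.756 on 40 df, a size of about 8.7%; 200,000 simulated trials gave 8.6%.

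If instead 3 patients per arm drop out at random during follow-up, mean replacement gives 5.8-6.3% on POD1, 8.4-9.2% on POD7 and 8.2-10.7% for group-by-time. If dropout depends on the PACU score in opposite directions by arm, POD1 reaches 16.1% with mean replacement and 10.1% with complete cases.

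**5. Other permitted routes.** With the same 3-per-arm loss and correlation 0.8 per day, under both random and score-dependent dropout, an unstructured mixed model gave 3.7-5.5% and multiple imputation 4.0-5.4%. The Monte Carlo error is about 0.35 to 0.55 percentage points.

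**The case against.** The strongest reply is that the plan commits to none of the faulty procedures. Section 8 does not mention arm-mean replacement, complete-case deletion or a pooled error for per-visit contrasts. Its imputation route admits multiple imputation, and its second route admits the very mixed model recommended here. That stands. A reader might infer that both stated routes give wrong error rates; step 5 shows that they need not.

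A reader might also blame the uneven visit spacing. Spacing alone does nothing. The distortion needs a non-spherical covariance left uncorrected, or unequal variances that are pooled.

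A third tempting argument counts patients with all four scores and sets that count against the 21 required. The comparison does not apply, because 21 was calculated for the single POD1 contrast and Section 8 does not propose complete-case deletion. Losing 3 per arm at POD1 leaves exactly 21.

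Holm-Bonferroni also softens the per-visit figures. Over four visits, the familywise rate under the first three SD settings in the table is 5.3-8.5%, against 4.2-4.9% with equal SDs. It reduces the damage but does not correct p-values that are already off.

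Finally, a POD1 test done on its own does not involve sphericity. That is true, but Section 8 does not say that POD1 will be tested on its own, and missing POD1 scores would still fall under the open rule.

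**Conclusion.** The point holds as a weakness in the choice and specification of the longitudinal analysis. It does not show that the planned analysis is invalid. The same wording admits tests near 5% and tests well away from it, with nothing to decide between them.

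The sizes in steps 2 to 4 are conditional. The pooled-error figures rest on assumed SDs and vanish when SDs are equal. The 7-8% for group-by-time rests on correlation that decays with time. The 8.6% rests on a single-value method the plan permits but does not name, with all 3 losses per arm falling at the tested visit. The 12.5% loss is inferred from 24 against 21.

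The improvement is still worth making. A mixed model needs neither sphericity nor equal variances, keeps every observed score, and removes the later choice at almost no cost.

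**What to change.** Replace the ANOVA and missing-data sentences in Section 8 with one analysis:

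- A mixed model for repeated measures of NRS, fitted by REML, with arm, time and arm-by-time, unstructured covariance and Kenward-Roger degrees of freedom. Name a fallback covariance structure in case of non-convergence.
- Use all observed scores of all randomised patients. Read the arm difference at each visit, with Holm-Bonferroni kept as planned.
- Rule out single-value imputation. State the missingness assumption, and use multiple imputation as a sensitivity analysis for missing POD1 scores.
- Reconcile Section 11.1, which leaves out data of subjects who withdraw early, with the intent-to-treat statement in Section 8. Otherwise the new model would contradict the protocol.

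The cost is text in Sections 8 and 11.1. SAS is already named, and no extra patients or visits are needed. The downside is a few more covariance parameters to estimate from 48 patients, which is why the fallback should be named in advance.
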